Pharmacokinetic analysis of the first 39 patients treated with fexinidazole in the DNDiFEX004 study showed that mean exposure to the M2 metabolite, the more active metabolite, in the cerebrospinal fluid was 2.6 times higher than the minimum inhibitory concentration used as the target value based on animal data collected in preclinical efficacy studies. Blood M1 and M2 concentrations were higher in patients than in healthy volunteers. The cerebrospinal fluid-to-blood ratio was around 31% for M2 and 52% for M1.
In order to provide the results within a reasonable timeframe, the study will be open label and will include a total of 125 children 6 years of age or older with a body weight of at least 20 kg. The patients will undergo the same assessments and investigations as the adult patients in Study DNDiFEX004. Under these conditions, if there are no statistically significant differences with regard to the efficacy and safety data, the results of treatment in children will be considered to be equivalent to those in adults. Thus, the number of children needed to treat is lower than if this had been a stand-alone study.
The objective is to be able to administer fexinidazole as a single treatment to all patients with HAT, without recourse to CSF-based staging of the disease. The aim of the present study is to assess the efficacy and safety of fexinidazole in children with stage-1, early stage-2 and late stage-2 HAT, stratified into three sub-groups. The study will provide an assessment of the success rate of treatment overall and by stratum, as well allowing for comparison with historical data on pentamidine in patients with stage-1 HAT.
 The dosing regimen is as follows: Body weight ≥ 20 kg and < 35 kg: 1200 mg from Day 1 to Day 4 600 mg from Day 5 to Day 10 Body weight ≥ 35 kg (same regimen as for adults) 1800 mg from Day 1 to Day 4 1200 mg from Day 5 to Day 10
 The objective of the study is to assess the efficacy and safety of an oral dosing regimen involving one daily intake for 10 days in the treatment of HAT due to T.b. gambiense at stage 1 or 2 in children 6 years of age or older weighing more than 20 kg. Primary Objective To demonstrate that the success rate 12 months after the end of treatment in patients with stage-1 or stage-2 HAT is greater than an acceptable rate of 80% and consistent with a target rate of 92%.

	

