1.10. Study DNDiFEX004 in Adults

The DNDiFEX004 study is entitled: "Efficacy and Safety of Fexinidazole Compared to the Combination Nifurtimox-eflornithine (NECT) in Patients with Stage-2 Human African Trypanosomiasis (HAT) due to *T.b. gambiense*: a Non-inferiority, Multicentre, Open-label, Randomised Pivotal Study"

As of 21 November 2013, 188 patients, i.e. around 125 patients receiving fexinidazole, had been randomised in the DNDiFEX004 study. No safety issues were identified on blinded data review. A total of 11 serious adverse events (SAEs) were reported, 3 of which were considered as possibly related to the IP and which resolved without sequelae. Overall, the safety profile was similar to that observed in earlier studies in healthy volunteers, and there were no treatment discontinuations. A meeting of the Data and Safety Monitoring Board (DSMB) was held. No safety issues were identified, and it was recommended to continue the study with the same design. No parasites were found in any patients at the End of Treatment (EOT) visit, based on blinded review, and no relapses were observed among 80 patients who attended their 6-month follow-up visit, with the exception of one patient whose health status had been poor at inclusion and who died shortly after leaving hospital (blind not lifted).

In the DNDiFEX004 study, fexinidazole is administered orally once daily after a meal: three 600-mg tablets per day for 4 days and then two 600-mg tablets per days for the next 6 days.

Pharmacokinetic (PK) analysis of the first 39 patients treated with fexinidazole in the DNDiFEX004 study showed that mean exposure to the M2 metabolite, the more active metabolite, in the CSF was 2.6 times higher than the minimum inhibitory concentration (MIC) used as the target value based on animal data collected in preclinical efficacy studies. Blood M1 and M2 concentrations were higher in patients than in healthy volunteers. The CSF-to-blood ratio was around 31% for M2 and 52% for M1.

Monitoring of biochemical parameters in all patients included in the DNDiFEX004 study did not show any increases in hepatic enzymes, as had been seen in healthy volunteers. As expected, a mild and reversible increase in creatinine was

observed in a small number of patients. The increases were grade < 2, and none were reported as adverse events (AEs).

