1.12. Rationale for the Study Design

Based on the encouraging efficacy and safety results in adults in the on-going DNDiFEX004 study, it would appear that oral treatment with fexinidazole could be beneficial in children 6 years of age and older. The dosing regimen in children is based on the results in adults (see Section 1.11 Choice of Dosing Regimen and Dose p 27).

This cohort of patients will provide additional efficacy data and, because the levels of systemic exposure in children are similar to those observed in adults, will show that the safety profile of fexinidazole, based on the data currently available, remains favourable.

The present study will be a plug-in to the pivotal DNDiFEX004 study in adults, which means that it will be possible to compare the results in the two studies since patients will be recruited simultaneously, i.e. same centres and investigators, with a genetically homogeneous population. In the same way, it will be possible to compare patients with stage-1 HAT in the present study to patients with stage-1 HAT in Study DNDiHATFEX005.

In order to provide the results within a reasonable timeframe, the study will be open label and will include a total of 125 children 6 years of age or older with a body weight of at least 20 kg. The patients will undergo the same assessments and investigations as the adult patients in Study DNDiFEX004. Under these conditions, if there are no statistically significant differences with regard to the efficacy and safety data, the results of treatment in children will be considered to be equivalent to those in adults. Thus, the number of children needed to treat is lower than if this had been a stand-alone study.

The objective is to be able to administer fexinidazole as a single treatment to all patients with HAT, without recourse to CSF-based staging of the disease. The aim of the present study is to assess the efficacy and safety of fexinidazole in children with stage-1, early stage-2 and late stage-2 HAT, stratified into three sub-groups. The study will provide an assessment of the success rate of treatment overall and by stratum, as well allowing for comparison with historical data on pentamidine in patients with stage-1 HAT.

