If the observed success rate is equal to or greater than 87.2% (\geq 109 successes out of 125 patients), or equal to or greater than 110 successes out of 126 patients (if the sample size is equal to 126), then the study is a success since the rate is significantly greater than 80% and consistent with the target success rate of 92%.

Conversely, if the observed success rate is less than 87.2% (\leq 108 successes out of 125patients) or less than 110 successes out of 126 patients, then the study is a failure since the success rate is significantly less than the target rate of 92% and consistent with the unacceptable rate of 80%.

The unacceptable success rate of 80% is greater than the success rate of melarsoprol at 12 months, i.e. 74.8%, because the success rates of the alternative treatments, i.e. NECT and pentamidine, are considerably higher than the rate with melarsoprol, which increases the level of unacceptability.

The target or expected rate of 92% is greater than the expected value of 89% set in the pivotal study, because the success rate is evaluated at 12 months instead of 18 months (expected gain of 1.2%) and also because the success rate reported in the pivotal study is encouraging, since only one failure (a patient whose health status had been poor at inclusion) among 150 patients was observed at the EOT, and no relapses were observed among 30 patients during the 6-month follow-up period (blinded data with an allocation ratio of 2 fexinidazole for 1 NECT).

It should be noted that, in the pivotal study, a 94% success rate was expected for NECT at 18 months, and the margin of acceptable difference was set at 13%. This means that the level of the unacceptable rate for fexinidazole is81% if the success rate for NECT is truly 94%, and 80% if the success rate for NECT was 93%. This also means that the various expectations and limits are consistent across studies.

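### The protocol treats a non-significant child–adult difference as equivalence, without a margin; the single-arm test limits the harm for efficacy, but nothing limits it for safety

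*Protocol*

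**What the plan says.** The rule appears twice, in the Study Rationale of the Protocol Summary and in section 1.12: "if there are no statistically significant differences with regard to the efficacy and safety data, the results of treatment in children will be considered" equivalent to the adult results. Section 1.12 then draws a design conclusion from it, that "the number of children needed to treat is lower than if this had been a stand-alone study". The study "will include a total of 125 children 6 years of age or older with a body weight of at least 20 kg".

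The comparison with adults is justified by the statement that "patients will be recruited simultaneously, i.e. same centres and investigators". Section 1.10 reports on the adult study: "As of 21 November 2013, 188 patients, i.e. around 125 patients receiving fexinidazole, had been randomised". Table 4 in Appendix 4 plans the first child's first visit for April 2014.

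The formal analysis is separate. Sections 9.1 and 9.8.1 test the children's 12-month success rate, single-arm, against 80% (unacceptable) and 92% (target). Section 9.8.3 pools late stage-2 fexinidazole patients from the pivotal study to look at the CSF white cell count, and pools DNDiHATFEX005 in a logistic model with stage and study as terms. Section 9.9 gives adverse event incidences with 95% confidence intervals. None of these sets a criterion for calling children and adults equivalent.

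**The concern.** A test of no difference is designed to detect a difference. When it fails to do so, the reason may be that the groups are alike or that the data are too few, and the p-value cannot say which. A rule that reads non-significance as equivalence therefore rewards imprecision: the fewer the children or the events, the easier the claim. The protocol goes a step further and cites the rule as a reason why fewer children are needed.

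At stake is the extension of adult efficacy and safety results to children, which is the purpose of the plug-in design. The criterion for it is fixed in the protocol, so this is not a detail left to the SAP. The premise of simultaneous recruitment also sits badly with the protocol's own dates.

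**Working it through.** **Inputs.** From the protocol: 125 children (9.1); about 125 adults on fexinidazole by 21 November 2013 (1.10); target success 92%, unacceptable rate 80%, success if at least 109 of 125 (9.8.1). Assumed, because the protocol does not give them: a two-sided Fisher exact test at 0.05; an upper adult number of 260; the true child rates; all adverse event rates.

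**1. The plan's own figure.** Exact binomial with X successes among 125:
- P(X ≥ 109 | 0.80) = 0.0243, the one-sided type I error.
- P(X ≥ 109 | 0.92) = 0.978, against the stated 97.5%.

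The stated power reproduces, and it comes entirely from the single-arm test.

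**2. Chance that the equivalence statement is met for efficacy.** For X ~ Bin(125, p_child) and Y ~ Bin(N, 0.92), sum P(X = x)·P(Y = y) over all pairs with Fisher p > 0.05:

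| True rate in children | N = 125 adults | N = 260 adults |
|---|---|---|
| 82% | 40.8% | 21.7% |
| 84% | 57.8% | 38.3% |

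At 82% and N = 125, an uncorrected chi-square test in place of Fisher gives 34.1%; at N = 260 it gives 19.1%.

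**3. Chance that the primary rule is met as well.** The same sum, restricted to x ≥ 109:

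| True rate in children | Primary rule alone | Both, N = 125 | Both, N = 260 |
|---|---|---|---|
| 82% | 7.7% | 7.2% | 6.9% |
| 84% | 19.9% | 18.6% | 18.1% |

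**4. Safety.** The same enumeration, with children at twice the adult rate of grade 3 or higher events:

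| Adults vs children | Missed, N = 125 | Missed, N = 260 |
|---|---|---|
| 10% vs 20% | 46.2% | 27.3% |
| 5% vs 10% | 76.5% | 59.7% |

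No second rule applies here.

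**5. Precision that could be reported instead.** If both groups are at 92%, the 95% half-width is 1.96·√[0.92·0.08·(1/125 + 1/N)], which is 6.7 points for N = 125 and 5.8 points for N = 260.

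**6. The 13-point margin.** Section 9.8.1 quotes this for fexinidazole against NECT in the pivotal study, where success was expected at 18 months. Applied to adults at 92%, it gives 92 − 13 = 79%, below the 80% this protocol calls unacceptable.

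**7. Dates.** About 125 fexinidazole adults were randomised by 21 November 2013; the first child is planned for April 2014. Those adults all precede the first child.

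**The case against.** The strongest reply is that the sentence is rationale text and drives no trial decision. It is not an objective, a hypothesis or the success rule, and section 9.1 derives the 125 from the single-arm test alone. That stands. A reader might infer from step 2 that the trial would succeed in 22% to 41% of cases with a 10-point shortfall; the documents do not support this, because most of those trials fail the 109-of-125 rule (step 3). Still, the equivalence sentence is not made conditional on that rule, the rule tests against 80% rather than against adults, and it says nothing about safety.

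A reader might also infer that section 9 contains no between-study comparison at all. That is too strong: the pooled model with DNDiHATFEX005 includes a study term, and section 6.3.4 compares pharmacokinetics between children and adults. What is missing is an analysis that implements or corrects the equivalence rule.

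Nor do the dates show that recruitment never overlapped. Section 1.12 calls the adult study ongoing and no end of adult enrolment is given. They show that overlap is at best partial.

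Finally, the adverse event rates in step 4 are illustrative, and section 9.9 already plans incidences with confidence intervals. That is fair, but those intervals are for the children alone and are not tied to the claim about adults.

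**Conclusion.** The rule is wrong as written and appears twice. Under the assumed Fisher test with adults at 92%, a true 82% in children would be called equivalent in 41% of trials with the documented adult number and in 22% with an assumed 260. For efficacy the practical exposure is smaller, because the primary rule also has to be met: about 7% of trials at a true 82%, and about 18% to 19% at a true 84%. For safety no second rule exists, and a doubling from 10% to 20% would be missed in 46% to 27% of trials, on assumed rates. The claim of simultaneous recruitment is overstated rather than false. The primary analysis and its sample size are unaffected. Severity: should be fixed.

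**What to change.** - In the Protocol Summary and section 1.12, delete the sentence that equates no significant difference with equivalence, and the inference that fewer children are needed. Let the sample size rest on section 9.1. Reword the recruitment statement to say that enrolment overlaps in part.
- In section 9.8.3, report the child-minus-adult difference in 12-month success with its 95% confidence interval, at the same timepoint and within the same disease stage. Repeat it for adults enrolled from April 2014, or adjust for enrolment period.
- In section 9.9, report child–adult differences in adverse event rates with 95% confidence intervals and make no equivalence claim.
- If a comparability claim for efficacy is kept, pre-specify and justify a margin for children against adults that does not admit a rate below the protocol's own 80% limit. With adults at 92% that means no wider than 92 − 80 = 12 points. The 13-point margin for fexinidazole against NECT should not be borrowed.

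The cost is wording in two places and a small amount of extra analysis. The price is a weaker claim: with a margin, comparability may not be shown even when children and adults are truly alike.

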1.13. Target Population

All children between 6 and 15 years of age (excluding upper limit) in whom parasites are detected in the blood, lymph or CSF will be included in the study. Only children who are able to swallow the tablets will be eligible for the study.

Given the limited number of children with HAT, all children in whom parasites are detected in the blood, lymph or CSF will be included, regardless of the stage of the disease.

The stages are defined as follows:

Patients with stage-1 HAT

- Trypanosomes in blood and/or lymph
- No trypanosomes in CSF
- CSF WBC ≤ 5/µL

Patients with early stage-2 HAT

- Trypanosomes in blood and/or lymph
- No trypanosomes in CSF
- CSF WBC > $5/\mu$ L and $\leq 20/\mu$ L

Patients with late stage-2 HAT

• Trypanosomes in blood and/or lymph

and

CSF WBC > 20/µL

Or

• Trypanosomes in CSF

An informed consent form, signed by the legal representative, i.e. one of the parents or the legal representative, will be collected for each child, and assent from the child will be collected in the presence of an impartial witness (see Section 14 Ethical Considerations; p 70).

2. Study Objectives and Endpoints

2.1. Objectives

The objective of the study is to assess the efficacy and safety of an oral dosing regimen involving one daily intake for 10 days in the treatment of HAT due to *T.b. gambiense* at stage 1 or 2 in children 6 years of age or older weighing more than 20 kg.

2.1.1. Primary Objective

• To demonstrate that the success rate 12 months after the end of treatment in patients with stage-1 or stage-2 HAT is greater than an acceptable rate of 80% and consistent with a target rate of 92%.

2.1.2. Secondary Objectives

- To verify whether the success rate varies depending on the stage of the disease; if the success rate is significantly different between the 3 strata, to show that the rate is greater than 80% and compatible with the historical success rate reported with NECT in patients with stage-2 HAT and with pentamidine in patients with stage-1 HAT.
- To verify whether the success rate of treatment with fexinidazole varies depending on the WBC count in the CSF prior to treatment initiation.
- To study changes in the success rate over time.

2.2. Study Endpoints

2.2.1. Primary Efficacy Endpoint

The primary efficacy endpoint is the outcome, i.e. success or failure, observed at the test-of-cure (TOC) visit, 12 months after the end of treatment (EOT).

Success at 12 months, adapted from WHO criteria (54), is defined as:

- Patient cured, i.e.:
 - o patient alive,
 - AND no evidence of trypanosomes in any bodily fluid,
 - o AND CSF WBC ≤ 20/μL.

A patient with no evidence of trypanosomes in any bodily fluid, but with CSF WBC > $20/\mu$ L, or who, in the opinion of the Investigator, requires rescue treatment will be considered as a probable relapse.

Patients lost to follow-up and retrieved after 12 months or patients who refuse to undergo lumbar puncture at 12 months will be considered as patients probably cured, i.e. successes, if they have no clinical signs or symptoms suggestive of HAT or if their symptoms can be clearly attributed to another aetiology, provided that the outcome was favourable at the last available assessment of HAT (6-month visit or subsequent unscheduled visit). If a patient is not assessed, i.e. has no lumbar puncture, at 12 months, but has a lumbar puncture or physical examination subsequently or at 18 months, the outcome at the latter visit will prevail over that at 12 months.

Patients who die due to any cause, patients lost to follow-up and not retrieved, and patients who refuse to undergo lumbar puncture at 12 months and whose clinical outcome had previously been assessed as unfavourable, i.e. probable relapse, will be considered as failures.

The prinicipal visit for assessment of the efficacy endpoint, i.e. success or failure, was set at 12 months after the EOT because the relapse rate between 12 and 18 months is very low and highly consistent across the various treatments administered to patients with stage-2 HAT (historical data). The success rate for melarsoprol was 74.84% at 12 months and 73.71% at 18 months, i.e. a relapse rate of 1.1% (n=3477), (61). The success rate for effornithine was 90.3% at 12 months and 89.1% at 18 months, i.e. a relapse rate of 1.2% (n=743), (61). The relapse rate for NECT was 1.4% (n=143) between 12 and 18 months after the EOT (43). Consequently, the overall relapse rate between 12 and 18 months after the EOT is around 1.2% for patients with stage-2 HAT, regardless of the treatment. The consistency of the findings suggests that the success rate at 12 months is predictive of the success rate at 18 months.

In addition, although the primary timepoint for assessment of the efficacy endpoint was set at 12 months after the EOT, patients will be followed until at least 18 months after the EOT.

2.2.2. Secondary Endpoints

Efficacy

Result (success or failure) at each visit from the end of treatment to month 18.

Safety Endpoints

Adverse events (AEs) will be graded according to the Common Toxicity Criteria for Adverse Events (CTCAE) of the National Cancer Institute (NCI), Version 4.03.

- Occurrence of any AEs grade ≥ 3, including laboratory abnormalities, during the observation period;
- Occurrence of any AEs, at any grade, during the observation period;
- Occurrence of any treatment-related AEs (grade ≥ 3 and any grade) during the observation period;
- Occurrence of any SAEs between the first intake of the IP and the end of the follow-up period (18 months).

ECG abnormalities with no clinical symptoms will not be reported as AEs. ECG changes will be analysed separately. If cardiac symptoms are present, information collected from ECG will be recorded in the eCRF.

PK Endpoints

Concentrations of fexinidazole, M1 and M2 in whole blood and CSF, and PK parameters derived from a population PK model.

 Samples of whole blood will be collected using dry blood spot (DBS) testing on venous puncture at the following timepoints:

- On Day 10, 3 hours and 7 hours 15 minutes after the last intake of fexinidazole;
- o On Day 11, i.e. 24 hours after the last intake of fexinidazole;
- o On Day 12, i.e. 48 hours after the last intake of fexinidazole.
- Lumbar puncture will be performed at Day 11, 24 hours after intake of fexinidazole for the EOT efficacy assessment in the first 30 patients. A dry CSF spot will be collected at the same time for PK analyses in the first 30 patients.

ECG Endpoints

Triplicate ECG tracings will be recorded at 2-minute intervals to assess QT interval at the following timepoints:

- At baseline
- On Day 4, 4 hours (H4) after intake of fexinidazole, on Day 4 H23 and on Day 10 two to three hours after intake of fexinidazole.

Triplicate ECGs and a safety ECG will be collected for different purposes and will be analysed separately (see Section 6.3.2 ECG Recordings; p 46).

3. Study Design

This is an open-label, multicentre, Phase II/III study. The study will be a plug-in to the pivotal study, DNDiFEX004, and will be performed at the same sites.

4. Selection of Study Population

To be eligible for inclusion in the study, patients must fulfil all of the inclusion criteria and none of the exclusion criteria.

